## 10.3 Part B: Exploratory Efficacy Evaluation of GX-188E + P

Part B of this study employs a Simon Two-Stage design to evaluate the anti-tumor efficacy of the investigational combination at the recommended Phase 2 schedule established as tolerable in Part A. In the first stage (Stage 1) of Part B, 15 patients will be treated. These may include any patients from Part A (1) who do not experience a DLT, (2) receive the recommended Phase 2 treatment regimen, and (3) who are considered evaluable for efficacy. If at least 3 efficacy evaluable patients from Part B Stage 1 (see Section 24.4) have objective responses by RECIST v1.1 criteria (partial response or better) within the first 24 weeks of treatment, an additional 13 patients will be enrolled, for a total of 28 efficacy evaluable patients. If 2 or fewer efficacy evaluable patients in Part B Stage 1 have an objective response, enrollment into the study will be discontinued for futility. Study has passed the first stage of Simon-Two stage design.

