#### Hematologic DLT:

- Grade 4 neutropenia [absolute neutrophil count (ANC)  $< 0.5 \times 10^9/L$ ]
- Grade 3 febrile neutropenia (ANC < 1.0 x  $10^9$ /L with a fever  $\ge 38.3^{\circ}$ C)
- Grade 4 thrombocytopenia ( $< 25.0 \times 10^9/L$ ) lasting > 4 days or that requires platelet transfusion
- Grade  $\geq$  3 thrombocytopenia associated with Grade  $\geq$  3 bleeding
- Any hematologic toxicity resulting in death (i.e. Grade 5)

In addition, any other AE that is felt to be treatment-limiting in the medical opinions of the Principal Investigator and the Sponsor's Medical Monitor may be considered a DLT. These include, but are not limited to the following:

- Any toxicity leading to more than one missed dose of either GX-188E or pembrolizumab during the DLT-evaluation period
- Any toxicity leading to > 2 weeks delay in initiation of the  $2^{nd}$  cycle of pembrolizumab

No additional patients will be enrolled until all patients in Part A have completed the DLT window and the investigational treatment regimen has been deemed safe. If  $\leq$  1 patient of 6 enrolled patients experiences DLT, enrollment into Part B will be initiated. If 2 patients experience a DLT, an additional 3 patients will be enrolled and evaluated for DLTs. If 3 or more patients in the first 6 or 9 patients experience a DLT, the combination at the current treatment schedule will be considered too acutely toxic and enrollment will begin at a reduced frequency treatment schedule (see Study Treatment Regimen, Treatment Reduction Plan). Depending on the occurrence rate of DLT, all patients without DLT, who receive the recommended Phase 2 treatment regimen, and who are considered evaluable for efficacy from Part A will be included in the first stage of Part B.

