## STATISTICAL METHODS

Maximum 60 patients are planned for enrollment into this clinical trial.

Safety Analysis. All patients who receive at least one dose of the investigational treatment will be included in the safety population. All safety analyses will be performed on the safety population. Adverse Events (AE) will be coded according to the MedDRA adverse event dictionary. The results will be tabulated to examine their frequency, organ systems affected, and relationship to study treatment. The results of laboratory tests will be evaluated similarly.

Efficacy Analysis. Efficacy results, including but not limited to ORR24, BORR, DOR, DCR, TTR, PFS, and OS for patients enrolled into Part A will be provided using descriptive statistics. Objective responses will be evaluated according to both RECIST v1.1 and Response Evaluation Criteria In Solid Tumors for Immunotherapeutics (iRECIST).

Note: Confirmatory scans are required for all determinations of objective response (PR or CR), Stable disease(SD) and disease progression (PD). Confirmatory scans must be performed at least 4 weeks later.

Part B follows a Simon Two-Stage mini-max design. The sample size for the first stage of Part B is 15 patients; the sample size for the second stage is 13 patients, for a total of 28 patients. Patients from Part A without a DLT, who receive the recommended Phase 2 treatment regimen and who are considered evaluable for efficacy will be included in the analysis for Part B Stage 1. For a null hypothesis ORR24 of 0.15 and an alternative hypothesis ORR24 of 0.35, the sample size of 28 subjects will provide a one-sided significance level of 5% and a power of 80%. For Stage 1, a minimum of three patients must demonstrate a response (PR or better) to proceed to the second stage. Study has passed the first stage of Simon-Two stage design. If Stages 1 and 2 are completed, a minimum of 8 patients must demonstrate a response (PR or better) to reject the null hypothesis. If a patient's responses could not be confirmed, that patient will not be included in the primary efficacy population for ORR24.

Part C is to evaluate efficacy in larger patient population.

In Keynote-158 study (pembrolizumab monotherapy in patients who have progressed with standard of care systemic therapy), ORR in total patients (i.e. regardless of PD-L1 status) and with CPS  $\geq 1$  were 12.2% and 14.6%, respectively.

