#### 10.2 Part A: Evaluation of Safety and Tolerability

Part A follows a standard 6 + 3 design and will establish the recommended Phase 2 treatment schedule for the investigational combination.

A minimum of 6 patients will be enrolled and treated at the Starting Schedule (see Table 3 in Section 12). If none or only 1 of the first 6 patients experiences a dose-limiting toxicity (DLT) (for protocol defined DLTs, please refer to Section 21), the study will move into Part B. If two patients experience a DLT, an additional 3 patients will be enrolled and evaluated for DLTs. If no additional patients experience a DLT (i.e. only 2 out of 9 patients have DLTs), enrollment into Part B will be initiated. If  $\geq$ 3 patients in 6 or 9 have a DLT, the Starting Schedule will be considered to be too toxic and enrollment into Reduction Level 1 (see Table 3 in Section 12) will be initiated. If one of the first 6 patients, or no more than 2 patients in a total of 9, experiences a DLT at Reduction Level 1, then this regimen will be moved into Part B of the study. If  $\geq$ 3 patients in 6 or 9 receiving Reduction Level 1 experience a DLT, then the

investigational regimen will be considered to be too toxic and no additional patients will be enrolled into the trial. Only one reduction in the treatment schedule is planned.

Patients without DLT who are treated with the recommended Phase 2 regimen and who are considered to be evaluable for efficacy will be included in the efficacy analysis for the first stage of Part B.

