#### 24.3 Sample Size and Power

**Part A Safety Evaluation:** For the traditional 6+3 design of Part A, the goal is to determine a treatment schedule for which the rate of DLTs is less than 33% in 6 or 9 patients. A minimum of 6 patients are planned for Part A, with a maximum of 18 DLT-evaluable patients for the Starting Treatment Schedule and Reduction Level 1. If  $\geq$ 3 in 6 or 9 patients at Reduction Level 1 have DLTs, then the investigational treatment regimen will be considered too toxic and enrollment into the study will be discontinued.

Part B: Part B follows a 1-sided Simon 2-Stage design; 15 patients, including all patients from Part A without a DLT, who receive the recommended Phase 2 regimen and who meet the criteria for the Efficacy Evaluable Population (see Section 24.4), with HPV 16 or 18 positive advanced cervical cancer will be included in the first stage analysis. If 3 or more objective responses (PR or better) are observed in the first stage, another 13 patients will be enrolled into the second stage, for a total of 28 patients in Part B. Study has passed the first stage of Simon-Two stage design. For a null hypothesis ORR24 of 0.15 and an alternative hypothesis ORR24 of 0.35, the sample size of 28 patients will provide a one-sided significance level of approximately 5% and a power of 80%. If Stages 1 and 2 are completed, a minimum of 8 patients must demonstrate a response (PR or better) to reject the null hypothesis.

Part C: Part C is to evaluate efficacy in larger patient population. In Keynote-158 study (pembrolizumab monotherapy in patients who have progressed with standard of care systemic therapy), ORR in total patients (i.e. regardless of PD-L1 status) and with CPS  $\geq$  1 were 12.2% and 14.6%, respectively.

Given this, null hypothesis for  $ORR_{24}$  was set at  $P_0 = 12.2\%$ . With an alternative hypothesis for  $ORR_{24}$  of  $P_a = 37\%$ , the sample size of 60 subjects was calculated considering two-sided significance level of 0.05, 97% power, and 25% dropout rate.

The confidence interval (CI) for ORR24 will be estimated using exact Clopper-Pearson method, and if the lower bound of the two-sided 95% CI for ORR24 exceeds 12.2%, it will be proven to satisfy the primary efficacy.

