#### 24.4 Analysis Populations

Safety Population. All patients who receive at least 1 dose of 1 agent in the investigational treatment regimen (i.e. either GX-188E or P) will be included in the analysis of safety, regardless of the duration of treatment.

DLT-evaluable. Unless doses are missed within the first two weeks of treatment (i.e., Week 1 Day -1 to Week 2 Day 7) due to DLT(s), a patient must receive all of the planned administrations of both agents (GX-188E and P) within the DLT-evaluation period to be considered evaluable for DLT. If a patient misses any treatment within the first two weeks of the study for reasons other than a DLT, the patient will be considered non-evaluable for DLT and replaced.

Efficacy Evaluable Population. All patients who discontinue the study treatment regimen early due to treatment-related toxicity will be considered evaluable for efficacy. Patients who discontinue study due to disease-related death, unequivocal tumor progression or with at least 1 post-baseline tumor assessment must have received at least 45 days of treatment to be considered evaluable for efficacy. Patients in Part B and C who do not meet the aforementioned requirements will be considered non-evaluable for response and may be replaced. Patients from Part A, who receive the recommended Phase 2 regimen and who meet the aforementioned criteria for the Efficacy Evaluable Population will be included in the analysis for Part B and C. The following table provides further, more specific details.

Table 7. Determination of Patients to be Included in Efficacy Evaluable.

Patient Cohort	Reason for Discontinuation	Number of Days on Protocol Treatment	Include in Efficacy Evaluable Population (Yes/No)?
Part A receiving RP2 regimen*	Protocol-Defined Dose Limiting Toxicity (DLT), or other toxicity	Not applicable	Yes, included in Efficacy Evaluable Population
Part A receiving RP2 regimen*	Disease-related death, unequivocal tumor progression or at least 1 post-baseline tumor assessment	< 45 days	No
Part A receiving RP2 regimen*	Disease-related death, unequivocal tumor progression or at least 1 post-baseline tumor assessment	≥ 45 days	Yes, included in Efficacy Evaluable Population
Part A, receiving dose > RP2 regimen*	Any	Not applicable	No
Part B and C	Disease-related death, unequivocal tumor progression, or at least 1 post-baseline tumor assessment	< 45 days	No, patient may be replaced

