## Part B. Exploratory Efficacy Evaluation in Advanced Cervical Cancer Patient (Simon Two-Stage Design)

In Part B, patients will receive the treatment schedule for GX188E + P that was determined from Part A to be well-tolerated. In the first stage of Part B, 15 patients with advanced HPV 16 or 18 positive cervical cancer will be treated. If at least 3 patients experience an objective response (i.e. partial response or better) by RECIST v1.1 in the first 24 weeks of treatment, an additional 13 patients will be enrolled for a total of 28 patients in Part B. If 2 or fewer patients in the first stage experience an objective response, enrollment into Part B will be discontinued for futility. Study has passed the first stage of Simon-Two stage design.

Sample Size for Part B: Part B follows a 1-sided Simon 2-Stage minimax design; 15 patients, including all patients from Part A without a DLT, who receive the recommended Phase 2 regimen and who meet the criteria for the Efficacy Evaluable Population with HPV 16 or 18 positive advanced cervical cancer will be included in the first stage analysis. If 3 or more objective responses (Partial response or better) are observed in the first stage, another 13 patients will be enrolled into the second stage, for a total of 28 patients in Part B. Study has passed the first stage of Simon-Two stage design. For a null hypothesis ORR24 of 0.15 and an alternative hypothesis ORR24 of 0.35, the sample size of 28 patients will provide a one-sided significance level of approximately 5% and a power of 80%. If Stages 1 and 2 are completed, a minimum of 8 patients must demonstrate a response (partial response or better) to reject the null hypothesis. If a patient's response could not be confirmed, that patient will not be included in the primary efficacy analysis for ORR24.

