#### 5.4. EFFICACY EVALUABLE POPULATION

All patients who complete the study will be included into the efficacy evaluable population. These patients will be identified by using the "Subject's status?" with answer "Completed trial" from end of study page of CRF.

All patients who discontinue the study treatment regimen early due to treatment-related toxicity will be considered evaluable for efficacy. These patients will be identified as those with DLT. Patients who discontinue study due to disease-related death, unequivocal tumor progression or with at least 1 post-baseline tumor assessment must have received at least 45 days on protocol treatment to be considered evaluable for efficacy. Patients who discontinue study due to disease-related death will be identified by using the "Primary reason for premature discontinuation from study" with answer "Death" from end of study page of CRF and the "Was death disease related" with answer "Yes" from death details page of CRF. Patients who discontinue study due to unequivocal tumor progression will be identified by using "Primary reason for premature discontinuation from study" with answer "Disease Relapse or Progression" from end of study page of CRF. Patients who discontinue study with at least 1 post-baseline tumor assessment will be identified as those with at least one RECIST/iRECIST Overall Response data on RECIST/iRECIST Overall Response page of CRF after screening visit. Patients in Part B and Part C who do not meet the aforementioned requirements will be considered non-evaluable for response and may be replaced. Patients from Part A, who receive the recommended Phase 2 regimen and who meet the aforementioned criteria for the Efficacy Evaluable Population will be included in the analysis for Part B and Part C. The following table provides further, more specific details.

Document: \\ieedc-vnac01\Biosdata\Genexine\GX-188E\GYA02599\Biostatistics\Documentation\SAP

Author: [name] Version Number: 1.1

Version Date: 05Sep2022

Template No: CS\_TP\_BS016 Revision 6 Reference: CS\_WI\_BS005

Analysis Plan Page 16 of 48

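### The plan bars Part A patients with a dose-limiting toxicity from Part B Stage 1 in some sections and counts them as efficacy evaluable for Parts B and C in others.

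*Protocol*

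**What the plan says.** **Rule 1, no DLT allowed.** Protocol 10.3 lists the conditions under which Part A patients count among the 15 Stage 1 patients, starting with "1) who do not experience a DLT, (2) receive the recommended Phase 2 treatment regimen". The same condition stands in:

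- the synopsis account of Part A: "all patients without DLT, who receive the recommended Phase 2 treatment regimen, and who are considered evaluable for efficacy from Part A";
- the synopsis statistical methods: "Patients from Part A without a DLT, who receive the recommended Phase 2 treatment regimen";
- Protocol 10.2: "Patients without DLT who are treated with the recommended Phase 2 regimen and who are considered to be evaluable for efficacy will be included";
- Protocol 24.3: "Part A without a DLT, who receive the recommended Phase 2 regimen and who meet the criteria for the Efficacy Evaluable Population";
- SAP 3.1, in both the Part A and the Part B text; the latter reads "including all patients from Part A without a DLT, who receive the recommended Phase 2 regimen".

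**Rule 2, DLT patients count.** Protocol Table 7 (section 24.4) has a row for Part A patients on the recommended regimen whose reason for discontinuation is "Protocol-Defined Dose Limiting Toxicity (DLT), or other toxicity". They are included in the Efficacy Evaluable Population whatever their time on treatment. SAP Table 1 repeats the row, and its footnote defines toxicity as any DLT. SAP 5.4 finds the patients who stopped for toxicity by their DLT status and then states: "Patients from Part A, who receive the recommended Phase 2 regimen and who meet the aforementioned criteria for the Efficacy Evaluable Population will be included". That sentence covers Parts B and C alike. Protocol 24.4 says the same. Neither makes an exception for a DLT.

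Protocol 24.5 computes ORR24 on the Efficacy Evaluable Population. SAP 3.3, which lists changes from the protocol, does not mention the point.

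**The concern.** A Part A patient who received the recommended regimen and stopped for a DLT is out of the Stage 1 set under Rule 1 and in the Part B analysis under Rule 2. The SAP holds both rules, so it cannot serve as the tie-breaker.

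Rule 1 selects on something that happens after treatment starts, and only in Part A. Under Table 7 a Part B or C patient who stops for toxicity stays in the denominator. If patients who stop early for toxicity respond less often, Rule 1 raises ORR24.

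The decision at stake is the Part B gate of at least 8 responders among 28, which opens Part C. The trial is open-label, and SAP 5 requires population membership only to be agreed before database lock. The choice could therefore be made with the affected patients' responses known.

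**Working it through.** **1. The plan's own design (Protocol 24.3).** Inputs: p0 = 0.15, p1 = 0.35; 15 patients in Stage 1, continue with at least 3 responses; 13 more patients; reject the null with at least 8 of 28. The probability of rejecting at response rate p is

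R(p) = Σ (x = 3 to 15) P[Bin(15, p) = x] × P[Bin(13, p) ≥ 8 − x].

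This gives R(0.15) = 0.0461 and R(0.35) = 0.8027, which match the stated alpha of about 5% and power of 80%. A full search for the minimax design returns the same one.

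**2. How many patients are affected.** Under Protocol 10.2 a schedule goes forward with at most 1 DLT in 6 patients or 2 in 9. Patients on a schedule above the recommended one are left out under both rules. The number affected, k, is therefore 0, 1 or 2. The documents do not give the observed count. As an assumption, let d be the true DLT probability. For the starting schedule the accepted outcomes have probabilities

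- no DLT: (1 − d)^6
- one DLT: 6d(1 − d)^5
- two DLTs: 15d²(1 − d)^4 × (1 − d)^3

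The chance of at least one DLT, given acceptance, is 44% at d = 0.1, 66% at d = 0.2 and 78% at d = 0.3. So k above zero is an ordinary outcome.

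**3. Worst-case effect on Part B.** Assume each included DLT patient takes a Stage 1 place and cannot respond, with the thresholds of 3 and 8 unchanged. Then

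R_k(p) = Σ (x = 3 to 15 − k) P[Bin(15 − k, p) = x] × P[Bin(13, p) ≥ 8 − x],

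where p is the response rate in the other 28 − k patients.

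| DLT patients in Stage 1 places | Alpha (p = 0.15) | Power (p = 0.35) | Stage 1 futility stop (p = 0.35) |
|---|---|---|---|
| 0 (Rule 1, or no DLT occurred) | 0.0461 | 0.803 | 6.2% |
| 1 | 0.0372 | 0.761 | 8.4% |
| 2 | 0.0295 | 0.713 | 11.3% |

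The largest gap in power between the rules is 0.803 − 0.713 = 0.090, or 9 percentage points. These figures describe the design before enrolment. The protocol states that Stage 1 has been passed, so the open Part B decision is the final count.

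**4. Part C.** Every no-DLT passage concerns entry to Part B Stage 1. For Part C the only stated rule is Rule 2. A DLT patient could thus be missing from the 28 and present in the pooled set, although no section says the two sets should differ in that way.

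**The case against.** **The passages can be reconciled.** On this reading the Efficacy Evaluable Population is the wider set, and absence of a DLT is an extra filter for Stage 1. But Protocol 24.4 and SAP 5.4 send all qualifying Part A patients into the Part B analysis as well as Part C, without a DLT exception. The reading fails for Part B.

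**Table 7 covers patients who stop for a DLT, not everyone who has one.** That is correct for the protocol; only SAP 5.4 equates the two groups. The conflict remains for those who stop.

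**The effect is small and would be visible.** This largely stands. At most two patients are involved, perhaps none, and Part B is labelled exploratory. SAP 15 also plans ORR24, BORR and DCR in the safety population as a sensitivity analysis, which contains every treated patient. That would show any effect, but it does not settle the primary set.

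**Readings that go too far.**

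- A reader might infer that 8/28 (28.6%) becomes 8/30 (26.7%). Part B is fixed at 28 evaluable patients, so the rules change who holds a place, not the denominator.
- A reader might infer that the Part C result turns on the rule, since 13/58 has a Clopper-Pearson lower limit of 12.51% and 13/60 one of 12.07%, against the 12.2% bound. That needs a Part C exclusion rule that no section states, patients left unreplaced although the final analysis is planned on 60 evaluable patients, exactly 13 responders, and two non-responding DLT patients. With one such patient, 13/59 gives 12.29% and still passes. At 11/45 (12.88%) and 11/47 (12.30%) both pass.
- A reader might take it as established that exclusion inflates ORR24. The documents say nothing about response in DLT patients, so this is plausible but assumed.

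**Conclusion.** The plan is wrong as written: two stated rules give different Part B sets for the same patient, and the SAP contains both. The direct consequence is confined to who fills the 28 Part B places and hence to the 8-of-28 gate. For Part C the stated rule is inclusion, and the fault there is that the Part B and pooled sets may not agree.

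The size is 0 to 2 patients. If no DLT occurred on the recommended schedule, nothing changes. The loss of up to 9 points of Part B power is a bound, reached only with two DLT patients who cannot respond. The direction of bias under the exclusion rule, towards a higher ORR24, rests on the assumption that these patients respond less often.

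**What to change.** Before database lock:

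1. Make the Table 7 and SAP Table 1 definition the single efficacy-evaluability rule for Parts A, B and C. It is the detailed definition, it treats toxicity alike in every part, and it is conservative if DLT patients respond less often.
2. Delete absence of a DLT as a condition for efficacy inclusion in the synopsis (Part A text and statistical methods), Protocol 10.2, 10.3 and 24.3, and SAP 3.1 (Part A and Part B text).
3. If Stage 1 was judged without any DLT patient, report the Stage 1 count and the 8-of-28 count both ways.

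The clinical DLT rules stay as they are. The cost is wording only, with no new patients, visits or data. ORR24 may come out slightly less favourable.

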## 10.4 Part C: Efficacy Evaluation in Larger Number of Patients

If at least 8 of the 28 subjects enrolled in Part B, experience an objective response who are considered evaluable for efficacy, it will be considered that ORR satisfies the criteria for study expansion and additional subjects will be enrolled in Part C to evaluate efficacy further in larger population. If only 7 or fewer subjects in Part B experience an objective response, enrollment to Part C will not open.

